## **February 2023 UPDATE: REVISED PHASE 2**

We will conduct a follow-up analysis of the data (revised Phase 2), which will include an analysis of the post-intervention period extending to the date that the Society of Obstetricians and Gynaecologists of Canada (SOGC) changes their labour management guidelines to reflect the ACOG/SMFM guidelines or 5 years beyond our original endpoint (*i.e.*, February 28, 2025), whichever occurs first.

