
**Study Design:** Cluster randomized controlled trial of a knowledge translation intervention of new guidelines for the diagnosis of poor progress in labor. The intervention will be randomized to centres (the clusters) in Alberta that provide intrapartum care, have facilities to perform cesarean section and deliver at least 70 primiparous women annually, with stratification based on facility type and geographic location. Clustering by centre and not individual caregivers (nurses/physicians) is necessary to prevent leakage or crossover of the intervention to controls. As all participating centres will eventually receive the intervention, the biostatistician will generate a randomization into two "waves". The intervention will be introduced sequentially by strata (Calgary, Edmonton, regional centres, rural centres) to the first "wave" hospitals in multi-week run-in periods after which those strata will be revisited for roll-out to the second "wave" hospitals.

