The labor culture survey will be an online survey, which will be emailed to physicians and nursing staff at intervention sites in fall 2019. The survey will be administered by Research Electronic Data Capture (REDCap), which is a secure, browser-based application designed to support electronic data capture. The Clinical Research Unit (CRU) in the Faculty of Medicine at the University of Calgary is the REDCap host.

**[April 27, 2020 update: Due to possible effects of the COVID-19 pandemic on the trial, an urgent steering committee meeting was convened on April 24, 2020. The decision was made to terminate the study as of February 29, 2020 (i.e., prior to the World Health Organization [WHO] declaring COVID-19 a global pandemic on March 11, 2020), instead of Phase I ending on November 30, 2019 and Phase 2 ending on November 30, 2021. This decision was made prior to the study team receiving the final data for the trial. The official statement of the steering committee regarding the end of the REDUCED Trial due to the pandemic can be found in Appendix 1. The dates in this version of the protocol reflect the new end date of the trial of February 29, 2020, and changes are bolded].**

Data collection will include retrospective (baseline) data for the two years prior to the roll out of the intervention (2015 and 2016) and will continue until 27 months after the completion of implementation for all sites (**February 29, 2020**). Intervention and post-intervention periods will be defined for intervention sites according to their dates of initiation and completion of implementation.

A random sample of obstetrical charts will be reviewed from the 13 intervention sites during the **27 month** period from Dec 1, 2017 to **February 29, 2020** to determine the percentage of cesarean sections for dystocia that were done following the ACOG/SMFM guidelines. A minimum of 50 charts per site will be reviewed. If there are fewer than 50 cesarean sections for dystocia at a given site, then all of the dystocia cases during the two-year period will be reviewed.

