### **Statistical Analysis**

The analysis will be conducted independently by the study statistician (RB). The primary outcome will not be changed during analysis. The trial with an explicit statement of the primary outcome will be registered at clinicaltrials.gov.

The primary analysis will include individual level data from all sites from the baseline period (2015 to 2016) and follow-up thereafter in both arms. The intervention period will be defined separately for each intervention site according to the date of completion of implementation of the program (which varied for the 13 intervention sites from January 31, 2017 to November 30, 2017). Data from the implementation phase (nominally one to two months) will be excluded as a wash-out period. The intervention period ends February 29, 2020 (27 months after completion of site initiation at all intervention sites).

CS rates will be assessed using repeated measures mixed effects logistic regression applied to individual births. We will apply a constrained baseline approach to adjust for pre-intervention data. Explanatory variables (fixed effects) in the model will include time period (in 6 month intervals), and indicators for intervention and post-intervention phases in the intervention sites. The post-intervention

parameter will represent the primary measure of efficacy. Corresponding site-specific random effects will be included for all fixed effects.

Having fewer than 40 sites, a small sample correction will be applied to the standard error for group differences underlying significance tests and confidence interval construction.

If the study has null results it will be important to try and determine if this were due to the ineffectiveness of the guidelines or poor adherence. Therefore, we also plan to assess indicators of guideline uptake such as changes in: duration of labor, time from admission until CS in non-progressing labors and rates of CS for dystocia <6cm.

Descriptive statistics will be used to characterize the labor culture at each site. We will use multiple linear regression to assess the relation between post-intervention percent change in cesarean section rate and site-level sub-scale means in the labor culture survey. In addition, we will examine the association between change in cesarean section rate and adherence to the guidelines for each site by simple linear regression.

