### Timeline

This project will be completed within 3 years. Transitioning control sites to intervention sites will begin **following the COVID-19 pandemic, if Phase 1 of the trial is considered successful.**

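### Does the revised Phase 2 need a written rule for control sites that take up the intervention during follow-up?

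*Combined protocol and SAP*

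**What the plan says.** The section headed February 2023 UPDATE: REVISED PHASE 2 is one sentence. It promises a follow-up "analysis of the post-intervention period extending to the date that the Society of Obstetricians and Gynaecologists of Canada (SOGC) changes their labour management guidelines" and caps it at February 28, 2025. It names no model and does not mention control sites.

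Three other places bear on the point.

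- **Moving the controls.** The Study Design paragraph under Background says "As all participating centres will eventually receive the intervention" and describes two randomised waves; "The intervention will be introduced sequentially by strata". The Timeline is later and narrower: "Transitioning control sites to intervention sites will begin" "following the COVID-19 pandemic, if Phase 1 of the trial is considered successful". Neither gives a calendar date.
- **The model.** Statistical Analysis, written for follow-up ending February 29, 2020, uses "indicators for intervention and post-intervention phases in the intervention sites", with completion dates that "varied for the 13 intervention sites from January 31, 2017 to November 30, 2017".
- **The dating of periods.** Data Collection says "Intervention and post-intervention periods will be defined for intervention sites according to their dates of initiation and completion of implementation".

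**The concern.** The Phase 2 window can run 60 months past the primary cut-off, and the protocol intends, at least conditionally, to treat the control sites at some time after that cut-off. The only written model has phase indicators in the intervention sites, described as 13 sites that finished implementation in 2017. Suppose that model were carried forward with its 2017 list of sites, and a control site moved in, say, 2023. Its later births would then be counted as control births. The contrast would partly set treated sites against treated sites, and a sustained effect could be misread as waning. The risk would arise when Phase 1 had succeeded, since success is the condition for the move. Sources of Bias names crossover to control sites as the main threat, but offers only monitoring for unexpected change, and a planned roll-out is not unexpected.

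**Working it through.** **1. What must be true for the bias to occur.** All of the following are needed, and the documents establish none of them:

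- Phase 1 is judged successful and the pandemic is over (Timeline). The Post-Implementation Phase section also ties spread to the remaining sites to extra operational resources.
- At least one control site moves before the SOGC change or February 28, 2025.
- Phase 2 is analysed as a between-arm contrast with the Statistical Analysis model unchanged.
- Sites that moved are still coded as control.

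**2. Which coding the text supports.** The Timeline speaks of control sites becoming intervention sites. Data Collection and Statistical Analysis define the periods of each intervention site by that site's own dates. Read together, a site that moves acquires its own wash-out and its own post-intervention indicator. The reference to 13 sites with 2017 dates describes the sites implemented for Phase 1; it does not exclude later ones. The cross-forward label in the Summary and the two waves in Study Design point the same way. No passage says this expressly for Phase 2, so it remains a reading.

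**3. Size if sites were left coded as control.** The plan gives no Phase 2 effect size to reproduce. Its design effect is 32% to 24%, i.e. 8 points, a risk ratio of 24/32 = 0.75 and an odds ratio of (0.24/0.76)/(0.32/0.68) = 0.671. The control sites number 26 − 13 = 13.

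Let *f* be the share of control-arm births in the window that follow a move. With an immediate full effect and equal-sized sites, the expected difference is 8 × (1 − *f*) points.

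The window has 27 months (December 2017 to February 2020) plus 60 (March 2020 to February 2025), 87 in all. All transition dates below are assumptions. If all control sites move on one date:

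| Assumed date | Treated control months | *f* | Shrinkage in the fuller model | 8 points becomes |
|---|---|---|---|---|
| None | 0 | 0 | 0% | 8.0 |
| January 2024 | 14 | 14/87 = 0.161 | 14-15% | 6.8 |
| January 2023 | 26 | 26/87 = 0.299 | 25-27% | 5.8-6.0 |
| January 2022 | 38 | 38/87 = 0.437 | 36-40% | 4.8-5.1 |

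The fuller model is a linear generalised-least-squares approximation to the planned analysis. It has 13 + 13 sites, January 2015 to February 2025, 6-month period effects, staggered 2017 starts after a 2-month wash-out, and random site, slope and site-by-period effects. The ranges cover assumed ICCs of 0.002 to 0.01, several variance ratios, and 8 to 100 births per site-month. If only 6 of the 13 controls move, shrinkage is about 7%, 12-13% and 17-19% for the same three dates.

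A separate check used a log-odds fit with site and 6-month-period effects, 14 periods after baseline and all controls moving for the last *k* of them. The log odds ratio is multiplied by (1 − *k*/14). With ln 0.671 = −0.399:

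- *k* = 2: exp(−0.399 × 12/14) = 0.710
- *k* = 4: exp(−0.399 × 10/14) = 0.752
- *k* = 6: exp(−0.399 × 8/14) = 0.796

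**4. Size under sensible handling.** Coding by actual exposure returns 0.671 in every one of these cases. In the fuller model, censoring each control site at its move returns the full coefficient in every setting. Relative to full untreated follow-up, censoring widens the standard error by at most about 4% (January 2024), 9% (January 2023) or 16% (January 2022).

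**The case for a change.** The strongest case for acting is that recoding, censoring and analysis by original allocation all fit the text and give different answers, and that this choice should not stay open until the data are seen. The SOGC end rule guards against national uptake of the guidelines but not against the trial's own roll-out. Two or three sentences would close the gap.

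The textual part of this stands. The Phase 2 section is silent, the arithmetic is sound, and Study Design (all centres) and the Timeline (only if Phase 1 succeeds) do not match. That mismatch matters only to whether any move happens. The Timeline wording is in bold, which the Table of Revisions associates with the April 2020 changes, so it appears to be the later and narrower statement.

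The rest is weaker. The Phase 2 text was added in February 2023 and clarified that November without mentioning any site that had moved. An end date tied to national adoption also makes most sense if the controls were then still untreated. That is inference, but it counts against the January 2022 scenario, which gives the largest figure. Nor is there one right rule. Censoring keeps the randomised comparison and loses some precision. Recoding keeps the data but relies more on the modelled period effects. Original allocation answers a legitimate intention-to-treat question about earlier against later roll-out.

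**Conclusion.** No change to the plan follows. The section leaves a detail unstated; it does not state a rule that gives a wrong result. Dilution requires a move inside the window and also an analyst who knowingly counts births at implemented sites as untreated. The protocol's own description of moved sites and site-specific dates steers away from that. An analyst who knows a site's roll-out date would recode or censor, and either removes the bias.

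The effect on Phase 2 is zero if no control site moves, or if moved sites are recoded or censored. Otherwise it cannot be determined from the documents. The 14-40% shrinkage across the three single-date scenarios rests on assumed dates, all 13 controls moving at once, an immediate full effect, no earlier SOGC stop and the least sensible coding. Only a follow-up analysis added after the trial ended is exposed. The primary analysis closes on February 29, 2020, before any planned move, and is unaffected.

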### **Economic analysis**

An economic evaluation will be conducted alongside the trial. The time horizon for the analysis will be to hospital discharge for both mother and baby. Costing will include the cost of the knowledge translation intervention implementation of the intervention including staff hours for participants and trainers, production of print materials, audit and feedback and also health care utilization during labor and delivery (CS rates, labor time, length of stay for mom and baby). The resource utilization, and costs, for costing the KT intervention will be collected by study team alongside the trial. Data on health care resource utilization, and the associated costs, will be collected as part of the trial from APHP and the Discharge Abstract Database of the Canadian Institute of Health Information. Outcomes will include maternal and neonatal morbidity/mortality, and patient experience also collected from administrative data.

### **Sources of Bias**

We anticipate that some reviewers would prefer a broader intervention aimed at multiple risk factors for CS. However, existing clinical trial data does not suggest that reducing exposure to commonly touted risk factors for CS such as labor induction, epidural anesthesia or continuous fetal heart rate monitoring are effective at preventing CS. Furthermore, a recent multi-centre clustered RCT in Quebec evaluated a comprehensive multi-modal program and were only able to reduce CS rates by 1.8%. Other complex strategies such as the active management of labor have also been ineffective at clearly reducing CS rates. We also anticipate that the simplicity of our intervention will improve adoption as increased complexity of an innovation has been shown to inhibit its adoption. The main source of bias in our study is contamination or crossover of the intervention to control sites which could make it difficult to demonstrate a change in the primary outcome. While possible we think this is unlikely as the vast majority of physicians providing maternity care in Alberta work at only one hospital and we do not anticipate large numbers will change hospitals over the course of the trial. None the less crossover is a real concern. However, our data will allow us to at least monitor if unexpected changes occur at control sites. Another possible source of bias is that practitioners will be insufficiently incentivized to change. Judging from the strong support we have seen so far from provider representatives we think this is unlikely. Furthermore, we will provide specific and meaningful incentives for providers such as reimbursement for time and continuing education credits.

### **Data Safety Monitoring Committee (DMSC)**

Data will be provided by AHP. The members will be [name] (Executive Director, Royal Alexandra Hospital), [name] (University of Calgary) and [name] (Director of the Research Centre of the CHUS hospital). These individuals have extensive knowledge of the subject and experience in clinical trials. The safety analysis will be performed for data up to June 30, 2018 as this is the midway point to the primary analysis.

### Timeline

This project will be completed within 3 years. Transitioning control sites to intervention sites will begin **following the COVID-19 pandemic, if Phase 1 of the trial is considered successful.**

## **APPENDIX 1**

### **REDUCED TRIAL STEERING COMMITTEE'S STATEMENT REGARDING THE END OF THE REDUCED TRIAL DUE TO COVID-19 PANDEMIC**

**(April 24, 2020)**

Given the impact of the COVID-19 pandemic, data collection for the REDUCED Trial will be considered ended on February 29, 2020 (i.e., prior to the World Health Organization [WHO] declaring COVID-19 a global pandemic on March 11, 2020), instead of Phase 1 ending on November 30, 2019 and Phase 2 ending on November 30, 2021.

Labour management post-pandemic has materially changed our ability to move forward with our research for a number of reasons. Currently, the physicians' and nursing staff's focus is on COVID-related issues, and we anticipate that caregivers and their patients will be less patient during labour. Furthermore, there are documents, such as the Calgary Zone Women's Health's *Patient Screening and Fever Management During COVID-19*, which includes guidance that is not congruent with the REDUCED guidelines (e.g., avoiding delayed pushing). Given the current environment, we do not think that this is an appropriate time to engage physicians and nurses about the trial guidelines, or physicians in audit feedback related to the trial. Furthermore, two of our sites (one intervention site and one control site) have temporarily closed their labour and delivery units during this time.
